A secondary objective of the study was to assess efficacy at each dose level based on (1) change in SARS-CoV-2 viral load from baseline (Day 1 prior to start of the study treatment) measured at Days 4, 7, 15, and 31; (2) time from baseline until undetectable SARS-CoV-2 viral load by reverse transcription polymerase chain reaction (RT-PCR); (3) mortality at Days 7, 15, and 31; (4) percentage of patients requiring invasive mechanical ventilation and/or ICU admission at Days 7, 15, and 31; (5) percentage of patients requiring non-invasive mechanical ventilation at Days 7, 15, and 31; and (6) percentage of patients requiring oxygen therapy at Days 7, 15, and 31. Results of these assessments, summarised in [Table 3](#), showed comparable results across the three dose groups. As progressive deterioration of respiratory function and development of cytokine release syndrome typically occur at a mean of 10 days from onset of COVID-19 symptoms⁴⁴, the endpoint of hospital discharge by Day 15 is considered to reflect successful amelioration of life-threatening complications.

Considering that dose groups were reasonably balanced for baseline characteristics, including age, gender, time from symptom onset to randomisation, comorbidities associated with increased susceptibility to complications from COVID-19 infection, disease severity at baseline, vital signs and laboratory assessments at baseline, and viral load at baseline, post-hoc analyses were performed to identify factors associated with hospital discharge by Day 15. Logistic regression analyses performed to assess a wide range of covariates for correlation with hospital discharge by Day 15 found that only the covariate of viral load at baseline was significantly correlated with

discharge rate. Additionally, covariates of 2.5-mg plitidepsin dose and age showed correlations that nearly reached significance. Consistent with results from the logistic regression analyses, differences in viral load at baseline were significantly correlated with efficacy outcomes, including use of oxygen therapy, use of invasive and non-invasive mechanical ventilation, and death, but viral load at baseline was not correlated with disease severity at baseline.

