2. OBJECTIVES AND ENDPOINTS

2.1. Objectives

Primary objective

- To compare efficacy of plitidepsin 1.5 mg or 2.5 mg *versus* the control assessing the need of supplementary oxygen.

Key secondary objective

- To compare efficacy of plitidepsin 1.5 mg or 2.5 mg *versus* the control assessing the time to sustained hospital discharge.

Secondary Objectives

- To compare efficacy of plitidepsin 1.5 and 2.5 mg *versus* control:
 - Assessing clinical status by the 11-category WHO Clinical Progression Scale⁴⁵ (See [Appendix 13 - World Health Organization \(WHO\) Clinical Progression Scale](#)).
 - In terms of the need of advanced oxygen support.
 - In terms of need for intensive care support.
- To compare safety/tolerability of plitidepsin 1.5 mg or 2.5 mg *versus* the control in terms of:
 - adverse events, adverse reactions and mortality.
 - abnormal laboratory parameters.
 - variations of vital signs.
 - ECG variations.

Other secondary objectives

- To compare efficacy of plitidepsin 1.5 mg or 2.5 mg *versus* the control in terms of:
 - hospital readmission related to COVID-19.
 - clinical evolution.
 - the need of supplementary oxygen.
 - the need of intensification of respiratory or intensive care support.
 - the need of intensification of pharmacological therapies.
 - superinfections.
 - mortality.
 - the evolution of viral load.
 - the evolution of inflammatory markers.
 - the immune response against SARS-CoV-2.
- To compare efficacy in the primary endpoint and describe safety/tolerability of pooled plitidepsin arms *versus* control.
- To compare efficacy in the primary endpoint and describe safety/tolerability between plitidepsin arms (1.5 *versus* 2.5 mg) in case both are significantly superior to the control.

- To explore the influence of risk factors or scores for clinical deterioration that were not individually included.
- To compare the results obtained before and after the change of the primary and secondary endpoint (protocol v.6 *versus* v.7).

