- Percentage of patients in each study group requiring non-invasive mechanical ventilation on Days 4, 8, 15, and 31.
- Percentage of patients requiring either extracorporeal membrane oxygenation ECMO or invasive mechanical ventilation by Days 4, 8, 15, and 31.
- Time to initiation with immune-modulating drugs.
- Time to initiation with antiviral drugs.
- Percentage of patients receiving subsequent immune-modulating drugs on Days 4, 8, 15 and 31.
- Percentage of patients receiving subsequent antiviral drugs on Days 4, 8, 15 and 31.
- Percentage of patients in each study group with nosocomial infection by Days 4, 8, 15 and 31.
- Mortality in each study group on Days 4, 8, 15 and 31.
- Change in SARS-CoV-2 viral load in each study group from Day 1 before administration of the study drug until Day 8.
- Percentage of patients in each study group with undetectable SARS-CoV-2 viral load on Day 8.
- Change in inflammatory biomarkers (C-reactive protein [CRP], ferritin, interleukin [IL]-6, IL-1 β , IL-10 and tumour necrosis factor alpha [TNF α]) in each study group from baseline until Days 2, 3, 4, 8, and 31.
- Change respect to baseline in individual serological assessments.
- Obesity, hypertension, age and individual co-morbidities included in the Charlson Index ([Appendix 11- Age-adjusted Charlson Index](#)), ISARIC-4C score ([Appendix 14 - ISARIC 4C Mortality & 4C Deterioration Scores](#)), or vaccination status.
- Time to sustained withdrawal of supplementary oxygen (11-category WHO Clinical Progression Scale \leq 4) with no subsequent reutilisation during remaining study period, before (protocol v.6) and after the amendment (protocol v.7).
- Time to sustained (i.e., with no subsequent readmission to Day 31) hospital discharge (since randomisation), before (protocol v.6) and after the amendment (protocol v.7).

Additionally, a dedicated QTc substudy will be performed in a subset of approximately 50 patients with ECGs collected over Days 1 to 3 using Holter monitors to assess treatment impact on QTc prolongation. See [Appendix 8](#) for objectives and respective endpoints planned for the QTc substudy. The substudy patients will have blood sampling for pharmacokinetic assessments over Days 1 to 4.

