4.1. Inclusion Criteria

Patients must fulfil all of the following requirements to enter the study:

1. Signed informed consent obtained prior to initiation of any study-specific procedures and study treatment.
2. Documented diagnosis of SARS-CoV-2 infection, determined by either qualitative polymerase chain reaction (PCR), antigen test by local laboratory or any other validated method approved by the local health authority, from appropriate biological samples collected no more than 72 hours prior to study treatment on Day 1.
3. Patient meets category 5 on the 11-point WHO Clinical Progression Scale ([Appendix 13 - World Health Organization \(WHO\) Clinical Progression Scale](#)): requires hospitalisation and oxygen by mask or nasal prongs/cannula.
4. A maximum of 14 days from onset of COVID-19 symptoms to initiation of study treatment on Day 1.
5. Male or female aged ≥ 18 years.
6. Adequate bone marrow, liver, kidney, and metabolic function, defined by the following tests performed at local laboratory:
 - Absolute neutrophil count $\geq 500/\text{mm}^3$ ($0.5 \times 10^9/\text{L}$).
 - Platelet count $\geq 75,000/\text{mm}^3$ ($75 \times 10^9/\text{L}$).
 - ALT and AST $\leq 3 \times$ upper limit of normal (ULN).
 - Serum bilirubin $\leq 1 \times$ ULN (or direct bilirubin $< 1 \times$ ULN when total bilirubin is above ULN).
 - Calculated creatinine clearance $\geq 30 \text{ mL/min}$ (Cockcroft-Gault equation).
 - CPK $\leq 2.5 \times$ ULN except if the patient has had recent (i.e, in the last week) shivering episodes or trauma. In that case, the level of CPK should be $\leq 5 \times$ ULN).
7. Agree not to participate in another interventional clinical trial through Day 31.
8. Females of reproductive capacity must have a negative serum or urine pregnancy test by local laboratory at study enrolment and must be non-lactating.
9. Females and males with partners of child-bearing potential must use effective contraception while on study treatment and for 6 months after last dose of plitidepsin. Patients in the control arm must use effective contraception at the time indicated in the approved product information (summary of product characteristics [SmPC] or leaflet). If no information is available in the approved product information, patients in the control arm must use effective contraception for at least one week after the study completion or the time indicated based on the investigator's discretion.

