 - The duration of the treatment does not exceed 72 hours prior to study treatment Day 1.
 - Prior administration of an antiviral might be acceptable in the following circumstances:
 - For small molecules (e.g., remdesivir, molnupiravir, nirmaltevir/ritonavir), they must have been given for an earlier stage of the disease, outside a clinical trial, and there should be a documentation of objective clinical deterioration plus evidence of persisting positivity for SARS-CoV-2 in appropriate biological samples. Last dose of previous antiviral drugs should have been administered at least 24 h before randomisation.

- For antiviral monoclonal antibodies, they must have been given for an earlier stage of the disease (including pre-exposure prophylaxis), outside a clinical trial, and there should be a documentation of objective clinical deterioration plus evidence of persisting positivity for SARS-CoV-2 in appropriate biological samples. Last dose of antiviral monoclonal antibodies should have been administered at least 1 week before randomisation.

6. Patients receiving treatment with chloroquine or derivatives within 8 weeks before enrolment or during the study.
7. Patients receiving treatment with strong CYP3A4 inhibitors or inducers ([Appendix 4 – Inhibitors and Inducers of CYP3A4](#)).
8. Viral illness (other than COVID-19) requiring therapy, except for patients with treated and adequately controlled (undetectable) human immunodeficiency virus infection.
9. Patients with uncontrolled known primary or secondary immunodeficiency, including chronic treatment with glucocorticoids (i.e., prednisone at a daily dose of >10 mg for >1 month, or another glucocorticoid at equipotent dose).

10. Any of the following cardiac conditions or risk factors:

- Sinus bradycardia (<50 beats/min), sinus nodal dysfunction (sick sinus disease), atrio-ventricular block of any degree (PR >200 msec), or any other bradyarrhythmia (<50 beats/min), except for patients with permanent pacemakers;
- Cardiac infarction, cardiac surgery or cardiac insufficiency episode within the last 6 months;
- Known abnormal value of left ventricular ejection fraction (LVEF <LLN), unless documented confirmation of recovery (LVEF >LLN) in the previous month;
- QT interval corrected using Fridericia's formula (QTcF) >450 msec for males or >470 msec for females;
- History of known congenital or acquired QT prolongation;
- Uncorrected hypokalaemia, hypocalcaemia (adjusted), and/or hypomagnesemia at screening;

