7.1. Efficacy Assessments

7.1.1. Test for COVID-19

Quantitative PCR to assess viral load on Day 1 before initiation of treatment and on Day 8 (± 1 day) (see Schedule of Assessments [[Appendix 5](#)]), will be performed by a central laboratory. Based on these assessments, changes in viral load from Day 1 to Day 8 will be calculated for each patient. The proportion of patients with undetectable SARS-CoV-2 on Day 8 will also be assessed.

Details regarding the collection, processing, storage, and shipment of oro-nasopharyngeal samples for qPCR testing will be provided to each investigational site before initiation of the study in the form of a laboratory manual. All oro-nasopharyngeal samples for qPCR must be processed and shipped as specified in the laboratory manual to maintain sample integrity. Any deviations from the processing steps (e.g., sample collection and processing steps, interim storage, or shipping conditions), including any actions taken, must be documented and reported to the sponsor. On a case-by-case basis, the sponsor may make a determination as to whether sample integrity has been compromised. Any deviation from the specified sample handling procedure that results in compromised sample integrity will be considered a protocol deviation.

Samples will be analysed using validated analytical methods, as approved by the sponsor.

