- 7 Coagulation:** D-dimer
- 8 Immunology:** Proinflammatory biomarkers (CRP, ferritin, IL-1 β , IL-6, IL-10, TNF α) in each study arm from baseline (Day 1 prior to start of the study treatment) to Day 4 and Days 8 (± 1 day), 15 (± 1 day) and 31 (± 3 days).
- 9 COVID-19 screen:** Qualitative PCR, antigen test to be performed by local laboratory, or any other validated method approved by the local health authority, from appropriate biological samples collected no more than 72 hours before study treatment on Day 1 for screening test to confirm COVID-19. In case more than one is available, the more recent one will be selected.
- 10 COVID-19 viral load:** Quantitative real-time reverse transcription polymerase-chain-reaction test (qRT-PCR) test to be performed by central laboratory from oro-nasopharyngeal exudate on Day 1 prior to initiating treatment and on Day 8 (± 1 day).
- 11 Chest imaging:** CT scan or x-ray will be done on Days 1, 8 (± 1 day) and 31 (± 3 days), Chest imaging performed within 48 hours of Day 1 is accepted and does not have to be repeated
- 12 Pregnancy test:** Serum or urine pregnancy test for females of child-bearing potential, to be performed by local laboratory for screening
- 13 Clinical Status:** Assessed using the 11-point WHO Clinical Progression Scale ([Appendix 13](#)) will be performed at screening, daily from Day 1 while hospitalised and on Days 8 (± 1 day), 15 (± 1 day) and 31 (± 3 days), where 0 = uninfected, no viral RNA detected; 1 = asymptomatic, viral RNA detected; 2 = symptomatic, independent; 3 = symptomatic, assistance needed; 4 = hospitalised, no oxygen therapy (if hospitalised for isolation only, record status as for ambulatory patient); 5 = hospitalised, oxygen by mask or nasal prongs; 6 = hospitalised, oxygen by NIV or high flow; 7 = intubation and mechanical ventilation, pO₂/FIO₂ ≥ 150 or SpO₂/FIO₂ ≥ 200 ; 8 = mechanical ventilation, pO₂/FIO₂ < 150 (SpO₂/FIO₂ < 200) or vasopressors; 9 = mechanical ventilation, pO₂/FIO₂ < 150 and vasopressors, dialysis or ECMO; 10 = dead.
- 14 Functional Status:** Assessed by the Barthel index score ([Appendix 7](#)); the pre-baseline (i.e., > 1 month prior to screening) functional status should be recorded, in addition to Day 1 prior to initiating study treatment, at hospital discharge, and on Days 8 (± 1 day), 15 (± 1 day) and 31 (± 3 days).

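### The Day 8 undetectable-viral-load percentage does not condition on the central Day 1 qRT-PCR, and the longitudinal model omits Day 1 load: probably a small dilution of the contrast, not bias

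*Protocol*

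**What the plan says.** **Endpoint.** Section 2.2 lists "Percentage of patients in each study group with undetectable SARS-CoV-2 viral load on Day 8" among the other secondary endpoints. Section 7.1.1 repeats it: "The proportion of patients with undetectable SARS-CoV-2 on Day 8 will also be assessed". Neither place asks for a detectable Day 1 value or a minimum fall. The objective it serves in Section 2.1 is efficacy in terms of "the evolution of viral load".

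**Entry.** Infection is documented by local qualitative PCR, antigen test or another validated method, "from appropriate biological samples collected no more than 72 hours prior to study treatment on Day 1" (Section 4.1). The symptom window is "A maximum of 14 days from onset of COVID-19 symptoms to initiation of study treatment on Day 1". There is no viral-load threshold. Patients with earlier antiviral treatment must also show "evidence of persisting positivity for SARS-CoV-2 in appropriate biological samples" (Section 4.2), which is still not a detectable central result on Day 1.

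**Baseline measurement.** The viral load itself is a separate "test to be performed by central laboratory from oro-nasopharyngeal exudate on Day 1 prior to initiating treatment" (Appendix 5), repeated on Day 8. It is not an eligibility test.

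**Analysis.** Sections 8.2 and 8.5 assign secondary efficacy endpoints that are not time-to-event to the FAS. Section 8.2.2 defines the FAS by one dose and one postbaseline clinical status. Section 8.5.3 plans between-arm comparisons of binary endpoints at Day 8. It also plans mixed-effect longitudinal models with treatment, time, stratification and time-by-treatment terms. Day 1 viral load is not among them.

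**The concern.** The objective is about change over time, but the percentage is a status at one time. A patient undetectable on both Day 1 and Day 8 shows no evolution of viral load and cannot show a drug effect, yet adds to the favourable count in whichever arm he or she was assigned to. Such patients raise the percentage in every arm by a similar amount and shrink the difference between arms. They also make the percentage harder to read, because some of those undetectable on Day 8 were so before the first dose.

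The information needed to separate them is already collected, since the central Day 1 sample is scheduled for every patient. The same sample is unused as a covariate in the listed longitudinal model, where it would be expected to improve precision.

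**Working it through.** The protocol gives no rate, effect size or power for this endpoint, so there is no stated figure to reproduce. The check has three steps.

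**1. Can a patient undetectable on Day 1 reach the analysis?** Yes. Entry uses a different test, a different laboratory and a sample up to 72 hours older. The FAS has no virological condition, and the endpoint does not refer to Day 1.

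**2. How many such patients might there be?** The share, q, is not stated. Section 1.1 gives the proof-of-concept baseline as 6.1 log10 copies/mL, range 1.5 to 10.6 (called a mean there and a median in Section 1.3). Assume a normal distribution. The range is 10.6 − 1.5 = 9.1. Dividing by about 4.4, the expected range in SD units for roughly 44 values, gives an SD of 9.1 / 4.4 = 2.07. The detection limit is also an assumption. The share below limit L is Φ((L − 6.1) / SD):

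| Assumed limit (log10) | SD 2.07 | SD 2.5 |
|---|---|---|
| 1.5 | 1.3% | 3.3% |
| 2.0 | 2.4% | 5.1% |
| 2.5 | 4.1% | 7.5% |
| 3.0 | 6.7% | 10.7% |

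A working range of about 1% to 10% follows.

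**3. What does that cost?** Assume that patients undetectable on Day 1 stay so on Day 8, and that among the others the Day 8 undetectable rate is 30% (control) v 43% (plitidepsin). Take 203 per arm (Section 8.1) and a two-sided 5% test. The observed rate in an arm is q + (1 − q)p, so the observed difference is (1 − q)(0.43 − 0.30).

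Power is Φ((d − 1.96·se0) / se1), where d is the difference, se0 the pooled and se1 the unpooled standard error. For q = 10%:

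- All patients: rates 0.10 + 0.90 × 0.30 = 0.370 and 0.10 + 0.90 × 0.43 = 0.487, so d = 0.117. Then se0 = √(0.4285 × 0.5715 × 2/203) = 0.0491 and se1 = √((0.370 × 0.630 + 0.487 × 0.513)/203) = 0.0488. Power = Φ((0.117 − 0.0963)/0.0488) = 66.5%.
- Detectable on Day 1 only: 203 × 0.90 = 182.7 per arm, d = 0.13, se0 = 0.0504, se1 = 0.0499. Power = Φ((0.13 − 0.0987)/0.0499) = 73.5%.

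| q | Difference, all patients | Power, all | Power, restricted | Gap | Control patients undetectable on Day 8 who were so on Day 1 |
|---|---|---|---|---|---|
| 0% | 13.0 points | 77.9% | 77.9% | 0 | 0% |
| 1% | 12.9 | 76.7% | 77.5% | 0.8 | 3% |
| 5% | 12.4 | 72.2% | 75.7% | 3.5 | 15% |
| 10% | 11.7 | 66.5% | 73.5% | 7.0 | 27% |

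The last column is q / (q + (1 − q) × 0.30). The restricted set has more power at every non-zero q shown, despite its smaller denominator.

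**The case against.** **It belongs in the statistical analysis plan.** Evaluable sets and covariates for such an endpoint are often fixed there, and Section 8 defers details to it. This stands in part, since that plan may refine the method. But the protocol itself assigns the endpoint to the FAS, plans the Day 8 comparison and lists the longitudinal model terms. The point concerns what is stated.

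**Baseline is already used.** The neighbouring endpoint in Section 2.2 is the change in viral load from Day 1 to Day 8, so the percentage is not the only test of antiviral action. If Day 1 is a modelled time point, the time-by-treatment term is itself a between-arm difference in change. Both points are fair. However, a change-score contrast is generally less efficient than adjustment for baseline, and it does nothing for the binary endpoint.

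**The size is speculative.** This stands. No detection limit or Day 1 share is documented. If the 1.5 log10 minimum was a measured value on a comparable assay, the main model gives about 1.3% and a loss of under one point of power.

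**Stronger readings that a reader might infer.** One is that the endpoint favours plitidepsin. It does not in expectation: Day 1 status precedes treatment and randomisation balances it on average, so only a chance imbalance could shift the result. Another is that phase 1 showed baseline load to predict viral clearance. Section 1.2 does say that "only the covariate of viral load at baseline was significantly correlated with" an outcome, but the outcome is hospital discharge by Day 15. A third is a severe loss of power. With 20% undetectable on Day 1 the same formula gives 55% v 68%, but 20% is nearly twice the highest share in the table (10.7%).

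**Conclusion.** The point holds as a low-priority matter of precision and interpretation. As the protocol stands, patients already undetectable on Day 1 count as favourable on Day 8, under an objective about change, and Day 1 viral load is absent from the listed longitudinal model. The treatment contrast is diluted by the factor (1 − q).

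For an assumed q of 1% to 10%, with 30% v 43% among the rest, the difference falls from 13 points to between 12.9 and 11.7. The loss is roughly 1 to 7 points of power compared with the restricted analysis. These figures rest on an assumed detection limit, an assumed normal distribution, assumed rates, and patients undetectable on Day 1 staying so.

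The text does not say that such patients have cleared the virus or responded. It reports a Day 8 status, and the reading as a favourable result comes from its place under an efficacy objective. The endpoint is an other secondary one, carries no power claim and is outside the multiplicity procedure, so the primary and key secondary conclusions are untouched.

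**What to change.** In Sections 2.2, 7.1.1 and 8.5.3:

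- Make the Day 8 between-arm comparison among FAS patients with a detectable central qRT-PCR on Day 1.
- Adjust that comparison, and the analysis of change in viral load, for Day 1 log10 viral load.
- Report the full-FAS percentage alongside, as descriptive.
- State before any unblinded analysis how patients without a valid central Day 1 result are handled, so that the denominator is not chosen afterwards.

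The cost is a change of wording and one covariate, because both samples are already scheduled. The downside is a slightly smaller denominator: at 5% undetectable on Day 1, about 193 per arm instead of 203. Restricting on a pre-treatment measurement keeps the randomised comparison valid.
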